4.3.3. Covariate Measures

The unique nature of this large inception cohort presents the opportunity to examine events that commonly occur in this population as both risks and outcomes. To that end, a number of events will be collected as covariate measures. Covariates that are available from the SVR trial, SVR II and annual visit forms include:

SVR and SVR II:

- Pre-Stage I: prenatal diagnosis, genetic syndrome, socioeconomic status, birth weight/gestational age, occurrence of neonatal shock.
- Stage I hospitalization: mechanical ventilation time, cardiopulmonary bypass and deep hypothermic circulatory arrest/regional cerebral perfusion times, ICU/hospital length of stay, delayed sternal closure, use of extracorporeal membrane oxygenation (ECMO), unplanned surgical/catheter interventions.
- Interstage, post stage II and post stage III: unplanned surgical/catheter interventions, cardiac arrest, ECMO.
- Stage II/Stage III: mechanical ventilation time, cardiopulmonary bypass and deep hypothermic circulatory arrest/regional cerebral perfusion times, ICU/hospital length of stay, delayed sternal closure, use ECMO, and unplanned surgical/catheter interventions.

Medical history data:

- Treatment with heart failure medications, (angiotensin converting enzyme inhibitors, angiotensin receptor blockers, beta-blockers), treatment for pulmonary hypertension, use of anticoagulants.
- New diagnoses: stroke, plastic bronchitis and protein losing enteropathy will be recorded.
- Weight and height will be measured at the time of the CMR and/or the exercise test.

Procedural history data:

- Unanticipated interventions: catheterization or surgery, (pacemaker implantation, stent implantation, Fontan revision, etc.), use of mechanical circulatory support, and lack of Fontan completion will be noted.

Socioeconomic (SES) data from the SVR and SVR II studies will be included as possible covariates in models for survival and ND outcomes. Educational status of the child, family structure, and language spoken in the home will be collected. In addition, maternal education level and current address information to determine census block variables such as percent within the census block living below the poverty level, will be collected at the time of ND evaluation to allow us to determine and adjust for the contribution of these factors to survival and ND outcomes at 11 years of age.

4.3.4. Schedule of Measurements

Table 2

Measurement	11 ± 1 years*	Annually to 16 years	One time visit after turning 16 years
Vital Status/Medical History including incidence of rhythm abnormalities	X	X	
CMR	X		
Echo	X		
Ramped Cycle Exercise Test	X		
ND Battery	X		
Biorepository Sample	X**		
Vital status			X

** or at study enrollment if >12 years at enrollment

* Included only if no prior adequate sample

4.4 Study Visits

All measures specifically performed for the SVR III protocol will be performed at study enrollment, ideally within a 2 year window defined by 11 years of age ± 1 year; however subjects can be enrolled at any time there is interest in participation up until September 30, 2020. As described above, the optimal window for the CMR and echo is within six months of one another, and comparison of these measures will only be performed if there has been no intervening cardiac operation or interventional catheterization. For those subjects who choose to complete the in-person evaluations within two consecutive days, Figure 1 demonstrates a reasonable schedule for accomplishing this.

Figure 1: Preferred Schedule of In-Person Evaluations

	8A	9A	10A	11A	12P	1P	2P	3P	4P
Day 1	Cardiac MRI		Exercise Test	Lunch		Echo			
Day 2	ND Battery			Lunch		ND Battery cont.			

Vital status and medical history will be performed annually beginning at age 10 years and through the conclusion of the study. The oldest participants will be 16 years of age at the time that the youngest participants reach the conclusion of the study window. An additional visit will

occur in 2024-2025 to identify vital status for all eligible to participate; all SVR survivors will be contacted to identify vital status, current contact information, location of current medical care, and potential questions they would like answered through further study.

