2. STUDY AIMS AND HYPOTHESES

2.1 Primary Aim:

To compare direct and indirect measures of right ventricular (RV) systolic and diastolic function between 11 year old subjects who had been randomly assigned to receive a right ventricular-to-pulmonary artery shunt (RVPAS) vs. a modified Blalock-Taussig shunt (MBTS) at the time of the Norwood operation.

Hypothesis: Assignment to the RVPAS compared to the MBTS will be associated with worse RV performance in subjects at age 11 years.

Primary Outcome: RV ejection fraction (RVEF) at 11 years, as measured by cardiac magnetic resonance (CMR).

Secondary Outcomes: Secondary outcomes will include additional measures of ventricular systolic, diastolic, and global function by CMR and echocardiogram (echo); anatomic measures related to RV function; and physiologic measures affecting RV function. Secondary outcomes of the greatest importance include:

- RVEF (measured by echo)
- RV fractional area change (measured by echo and CMR)
- Cardiac output (measured by CMR)

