Cardiopulmonary exercise testing will be performed with a standard ramp cycle ergometry protocol.^{45,46} Inclusion in this portion of the study will require participants be able to comfortably reach the pedals enough to effectively pedal the cycle ergometer". This typically, but not always correlates with a height of >/=130 cm.

Electrocardiographic monitoring and breathing by using expiratory gas analysis will be performed throughout the exercise test. Heart rate, blood pressure and oxygen saturation will be monitored continuously. Baseline inspiratory and expiratory flow volume loops will be performed. Subjects will then perform hyperventilation for 10 seconds (3 times for reproducibility) to measure maximal voluntary ventilation. Participants will then pedal in an unloaded state for 3 minutes. Workload will then be increased continuously with exercise watts ramped to achieve each predicted maximal work rate in watts after 10 to 12 minutes of cycling.

All subjects will be encouraged to exercise to exhaustion. This method is safe and allows for adjustment of work rate to optimize performance potential for each individual within 10-12 minutes. VO₂ max will be defined as the highest VO₂ achieved by the subject during the exercise stress test. Maximal aerobic effort will be defined as a peak respiratory exchange ratio (VCO₂/VO₂) of ≥ 1.10 . VO₂ max will be indexed to body weight and expressed as a predicted value for healthy age/gender matched subjects per Cooper and Weiller-Ravell.⁴⁷

In addition to VO₂ max, oxygen pulse (maximum VO₂/peak heart rate), and ventilator aerobic threshold (VAT) determined by V-slope method and confirmed by the dual criteria measurements of the ventilatory equivalents of CO₂ and O₂ (VE/ VCO₂ and VE/ VO₂), will be measured/calculated. The battery of exercise measures will include:

1. Maximal work rate: expressed in Watts
 - The maximal work rate reached during exercise test
2. Oxygen consumption (VO₂): expressed in ml/kg/min
 - Resting
 - Maximal –defined as highest oxygen consumption achieved during the exercise test when averaged over 10 second intervals
3. VAT will be measured by V slope method and confirmed with ventilator equivalent method
 - VO₂ at VAT
 - Percent of achieved maximal oxygen consumption (VO₂ at VAT/ max VO₂) x 100
4. Oxygen Pulse measured at rest, VAT and Max VO₂
5. Pulse Oximetry measured at rest, VAT and maximal exercise
6. Heart Rate measured at rest, VAT and maximal exercise

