7.1.2. Analyses of Secondary Outcomes

7.1.2.a Additional Measures of the Primary Aim

For all additional CMR and echo measures related to Aim 1, the distribution of each measure will be assessed. Continuous measures will be compared between randomized shunt types with either a Student's t-test or a Wilcoxon rank sum test as appropriate. Categorical measures will be compared with a Fisher exact test, Chi-square test or the Mantel-Haenszel test for trend.

In addition, subjects with CMR and echo performed within a 6 month window without an intervening cardiac procedure will be selected to assess the agreement between the two techniques. The continuous measures will be compared using Bland-Altman limits of agreement and Pearson's correlation coefficient. The Kappa statistic will be used to evaluate the agreement in the categorical measures in Echo and CMR.

7.1.2.b Secondary Aim 1: To compare the long-term death/transplant rates of subjects randomized to receive either a RVPAS vs a MBTS

Transplant-free survival rate will be calculated using the Kaplan-Meier method. The logrank test will be performed to determine if time since randomization to the composite endpoint of death or transplantation is different between the two shunt types. Cox proportional hazard regression will be used to model the time to death or transplant by shunt type; to determine if the shunt difference varies by time and to identify risk factors of the endpoint.

In addition, nonparametric competing-risks methodology will be used to estimate the cumulative incidence rate of death and transplant. Proportional subdistribution hazards model will be fit to assess the effect of covariate on death and transplant in a competing risk setting.

7.1.2.c Secondary Aim 2: To compare exercise tolerance between those randomized to receive a RVPAS vs a MBTS

VO₂ max, work rate VAT and items 4-11 from section 4.3.2.b, from ramped cycle ergometry will be compared between the two shunt groups. The distribution of the variable will be determined with descriptive statistics. If the variable is normally distributed, Student's t-test will be used to compare shunt groups. If non-parametric, then Wilcoxon Rank-Sum will be used.

7.1.2.d Secondary Aim 3: To compare the incidence of atrial and ventricular arrhythmias between those randomized to receive a RVPAS vs a MBTS at the time of the Norwood operation

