7.4 Interim Analyses and Stopping Rules for Termination of the Study

As this is an observational study and inclusion of the entire cohort will be valuable, there are no preconceived stopping rules for early termination of the study. However, we would like to reserve the right to look at an interim analysis at some time point such as when all participants have reached 10 years of age (2018). Premature termination of this study may occur because of a regulatory authority decision, or withdrawal of study approval by clinical site IRBs. In addition,

NHLBI retains the right to discontinue the study prior to the inclusion of the intended number of subjects, but intends to exercise these rights only for valid scientific or administrative reasons.

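### Measures labelled as age-11 outcomes may be taken at any age from 10 to about 16, but RVEF and the unindexed exercise measures are compared by shunt with no age term

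*Combined protocol and SAP*

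**What the plan says.** **Target age.** Section 2.1 defines the primary outcome as RVEF by CMR at 11 years. Section 2.2 places the exercise hypothesis at the same age.

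**Permitted age.** Section 4.4 schedules the in-person measures at enrolment, "ideally within a 2 year window defined by 11 years of age ± 1 year", and then allows that "subjects can be enrolled at any time there is interest in participation up until September 30, 2020". A footnote to Table 2 (section 4.3.4) also provides for measurement "or at study enrollment if >12 years at enrollment". The footnote markers in that table look interchanged, so I rely on section 4.4 for the rule. Section 4.4 also states: "The oldest participants will be 16 years of age at the time that the youngest participants reach the conclusion of the study window".

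**Exercise scales.** Section 4.3.2.b indexes VO2max to body weight and expresses it against predicted values for age and sex. The same list has "Maximal work rate: expressed in Watts", and it gives no index for oxygen pulse, minute ventilation or tidal volume. Maximal work rate is a named Aim 2 outcome in section 2.2; the other three are not.

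**Analysis.** Section 7.1.1 compares RVEF by shunt with a t-test or rank-sum test. In section 7.1.2.c, VO2max, "work rate VAT and items 4-11 from section 4.3.2.b, from ramped cycle ergometry will be compared between the two shunt groups", by the same kind of test. Neither section names age as a covariate, and no sensitivity analysis covers tests done outside 10 to 12 years. The one adjustment specified for comparing a measured, non-survival outcome by shunt is socioeconomic status, for the neurodevelopmental scores (section 7.1.2.e).

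**The concern.** Two separate things are at stake.

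**Precision.** Work in Watts, tidal volume, minute ventilation and oxygen pulse can be expected to rise as a child grows. If ages at testing are spread widely, that growth becomes noise in an unadjusted comparison.

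**Meaning of the RVEF result.** Section 3.2 gives as the study's motive that RV dysfunction after the RVPAS may be progressive. If so, the shunt difference changes with age at scan. An unadjusted mean difference is then an average over whatever ages happened to be scanned, not the difference at 11. Randomisation does not remove this, because identical age mixes in both arms still give an average over an unplanned age distribution.

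**Working it through.** **1. Age range.** Section 7.4 dates the whole cohort's reaching age 10 to 2018, so the youngest reach 12 in 2020, the year enrolment closes. Section 4.4 puts the oldest at 16 at that point. The permitted range is therefore 10 to about 16. This is a ceiling: the same dates make the oldest about 11 in 2015, when the study starts (section 1.2), so nobody had to miss the window. The documents do not say how many were tested late.

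**2. The plan's own power figure.** Inputs from section 7.3 and Table 4: 143 and 96 participants, SD 10, difference 4 points, two-sided alpha 0.05.
- Standard error = 10 × √(1/143 + 1/96) = 1.319.
- Noncentrality = 4 / 1.319 = 3.03, on 237 degrees of freedom.
- Power from the noncentral t = 85.5%, as stated.

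**3. RVEF precision.** The documents give no slope of RVEF on age, so slopes b of 0.5, 1 and 2 points per year are assumed. Treat SD 10 as the residual SD and ages as uniform, so that age SD = range / √12. Then total SD = √(100 + (b × age SD)²).

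| b (points/year) | Ages 10–12 (age SD 0.58): total SD, power | Ages 10–16 (age SD 1.73): total SD, power |
|---|---|---|
| 0.5 | 10.00, 85.5% | 10.04, 85.3% |
| 1 | 10.02, 85.4% | 10.15, 84.5% |
| 2 | 10.07, 85.1% | 10.58, 81.4% |

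Against 85.5%, the loss over 10–16 is 0.2, 1.0 and 4.1 points.

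Table 4 takes SD 10 from the Fontan Cross-Sectional Study, whose participants were aged 6 to 18 (section 3.3.1). Age spread is therefore probably already in that SD. In that case the stated power need not fall, and adjustment is a small gain. With residual SD = 10 × √(1 − r²) and assumed age correlations r of 0.1, 0.2 and 0.3, power is 85.9%, 86.9% and 88.6%.

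**4. RVEF target age.** Suppose the shunt difference changes by g points per year and both arms have the same age distribution. Then the unadjusted difference = difference at 11 + g × (mean age − 11). With ages uniform over 10–12 the mean is 11 and the shift is zero. Over 10–16 the mean is 13 and the shift is 2g: 1 point for an assumed g of 0.5, beside a design difference of 4 points.

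**5. Unindexed exercise measures.** If age explains a share R² of the variance, adjustment multiplies the residual SD by √(1 − R²), which is equivalent to a sample of N / (1 − R²). From N = 239, assumed R² of 0.1, 0.2, 0.3 and 0.4 give 239/0.9 = 266, 239/0.8 = 299, 239/0.7 = 341 and 239/0.6 = 398. The documents give no R², effect size or power for these measures.

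**The case against.** The case against is substantial, and most of it limits the size of the point.

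- **A reader might infer that Aim 2 as a whole loses power.** The documents do not support this. The exercise outcome that section 7.3 powers is percent-predicted VO2max, which is already scaled for age. Borrowing its effect of 6/16 = 0.375 SD at 143/96 gives 80.8% power, rising to 84.7%, 88.6%, 92.3% and 95.5% at R² of 0.1 to 0.4. The arithmetic is right, but the effect belongs to a different scale, every R² is assumed, and 143/96 is the CMR count. The stated figure of about 85% reproduces at totals of 265 to 269 (84.6% and 85.2%).
- **A reader might infer that RVEF needs a body-size term.** It does not. Section 4.3.1.a defines it as a ratio of volumes.
- **A reader might infer bias between arms.** Age spread alone does not bias a randomised comparison. Bias would need age at testing to differ by arm, and nothing in the documents says that it does. The plan does not, however, say that this will be checked.
- **An additive age term cannot deliver an age-11 effect.** This is correct. Such a model gives the same shunt difference at every age; an age-specific difference needs a shunt-by-age term.
- **Body size at testing comes about 11 years after randomisation.** This is also correct. If shunt type affects growth, adjusting for height or BSA could remove part of the effect being studied, so such adjustment should not be the main analysis.

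What remains is the open upper age, the absence of any age term, and four unindexed measures, one of them a named outcome.

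**Conclusion.** The point holds as a minor improvement. The plan labels outcomes as age-11 results, permits testing up to about 16, and compares RVEF and four unindexed exercise measures without age.

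For RVEF the precision at stake is about 0 to 4 points of power. That rests on assumed slopes of 0.5 to 2 points per year and on ages spread evenly to the ceiling, and it may already be absorbed in the planning SD. The more useful gain for RVEF is clarity about the age to which the result refers; whether the shunt difference does vary with age is conjecture at this stage. For work rate, oxygen pulse, minute ventilation and tidal volume, the gain could be larger but cannot be fixed from the documents. VO2max is unaffected.

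**What to change.** 1. **Unindexed exercise measures:** compare them by linear regression on randomised shunt with age at assessment as a covariate. Give a version that also adjusts for height, or that uses an indexed or predicted scale, as a secondary analysis only, with the reason stated (body size is post-randomisation and may be affected by shunt).
2. **RVEF:** include age at assessment as a covariate, and add a sensitivity analysis limited to scans at 10 to 12 years. If a difference at age 11 is to be reported, centre age at 11 and fit a shunt-by-age term, labelled exploratory and of low power.
3. **Reporting:** tabulate age at testing by arm, with the number tested after 12.

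The enrolment rule can stay as it is. Age follows from the visit date, height and weight are measured at the CMR and/or exercise visit (section 4.3.3), and section 7.6 provides for a revised statistical plan. The cost is a little more analysis, and the simple two-sample test is no longer the main analysis for these measures; it can be kept as supporting.

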4.5 Repeat Study Evaluations

If any of the evaluations are deemed incomplete either at the clinical site if the relevant imaging core lab assesses and finds that the images are inadequate, the evaluation may be repeated by the site if the patient, family and site personnel all agree to repeat the assessment.

5. SELECTION AND WITHDRAWAL OF SUBJECTS

5.1 Subject Inclusion:

All SVR study cohort members will be contacted to assess for vital status. Transplant free survivors will be approached to participate in the in-person assessment.

5.2 Subject Exclusion:

We will exclude patients who have undergone cardiac transplantation or biventricular conversion from all outcomes other than vital status. Those with pacemakers will be excluded from the CMR, and patients unable to comfortably reach the exercise bike pedals enough to effectively pedal the cycle ergometer will be excluded from the exercise test.

5.3 Subject Withdrawal Criteria

Subjects may withdraw from the study at any time if:

- Subject, parent, or legal guardian declines further participation.
- The investigator or physician judges that it is in the subject's best interest to withdraw from the study.

If the subject refuses to continue with the study visits, every attempt should be made to continue contact by telephone, written communication, or record review of vital status and medical history outcomes unless the subject specifically refuses such follow-up.

5.4 Subject Availability

Through the SVR and SVR II studies vital status has been collected annually for the entire SVR cohort. As of June 2014, 352 subjects were alive, 18 had undergone cardiac transplantation, and 3 had undergone biventricular conversion, leaving 331 transplant-free survivors with single ventricle physiology. Conservatively assuming only 80% retention of this cohort secondary to additional mortality, transplantation or loss to follow-up, we anticipate at least 264 participants will be available for this study to participate in the proposed protocol.

[figure not shown]
5.5 Recruitment/Enrollment Procedures

The ideal study window will extend from 10 to 12 years of age for each participant (11 years \pm 1 year), but subjects can be enrolled at any time there is interest in participation up until September 30, 2020. The Principal Investigator (PI) at each site, his or her designees, and the study coordinator will be responsible for subject recruitment. Parents/guardians of participants will be contacted by the team up to 6 months prior to the opening of the study window to introduce families to the study and to coordinate participation in all relevant portions.

Consents for the SVR and SVR II studies include ongoing permission to contact the families up to patient age 11 years. A letter will be mailed out to the families of eligible participants briefly describing the SVR III study. After approximately 2 weeks, we will telephone or email potential participants to discuss the study and address questions. The consent document will be mailed out to each family who has expressed interest in SVR III participation and the information will be reviewed subsequently by phone by the site PI and /or the research coordinator. Subjects may also be contacted in person at the time of a clinic visit at the study center. Data on all screened subjects will be entered into the screening log.

Initial consent, enough to schedule the evaluations, will be granted by interested families over the phone or in-person if contacted through the clinic. Neurodevelopmental questionnaires can be completed in advance of the study visit based upon this initial phone consent. If an in-person signature is required prior to completion of parent and /or teacher questionnaires by a site, then these questionnaires can be completed at or after the in-person evaluation. The written consent and assent documents will be reviewed in person with the parent/guardian and patient by the site PI/study coordinator and will be signed in person. If the interested subject/families are interested in remote participation only, consent will take place over the phone or virtually depending on the sites approved procedures.

Figure 2: Approach to Consent and Study Retention

Details of the Consent/Accent Process:

The consent process may vary slightly depending on the specific site. In general, we anticipate a multistep process:

- 1) A letter will be mailed to each survivor of the SVR cohort to briefly describe the SVR III study and plans for contact.
- 2) After two weeks, the family will be contacted via telephone or email to address questions and assess general interest in SVR III.
- 3) If the participant has undergone a transplant, consent will be mailed to renew the plans for annual follow-up for vital status.
- 4) If the participant is eligible and interested for the in-person SVR III study, appointments will be scheduled for the in-person evaluation in accordance with the needs of the family, and dependent on the institutions guidelines for in-person visits based on the COVID-19 pandemic.
- 5) If the participant is eligible and interested in remote participation in SVR III study, phone/virtual consent and discussion on what study events to be done remotely (ND Questionnaires, annual follow-up for vital status) will be held.
- 6) All questions from the parent/guardian and participant related to study participation will be thoroughly addressed by the site PI, his or her designees, and/or the study coordinator prior to signing and documentation of the informed consent/assent documents.
- 7) All signatures and dates will be accurately documented. Any errors will be noted in a note or memo. If mistakes have occurred re-consent/ re-assent may be performed if necessary.
- 8) Neurodevelopmental questionnaires can be completed before the actual visit and delivered to the study team at the time of the in-person evaluation based on phone consent. They can also be completed at or after the time of the in-person visit and mailed to the study team.

